14.1.7 Adverse Events of Special Interest (AESI)

“Adverse events of special interest” (AESIs) are defined in the study protocol (Section 10.1.3) to include:

- Status epilepticus
- Status epilepticus is defined to comprise the following MedDRA preferred term: status epilepticus.
- Hydrocephalus (communicating and non-communicating)
- Hydrocephalus is defined to comprise the following MedDRA preferred terms: hydrocephalus, congenital hydrocephalus.
- Meningitis
- Meningitis is defined to comprise the MedDRA preferred terms presented in [Appendix 5](#).
- Unexpected rapid decline on CLN2 scale not attributable to other causes
- This will be identified by clinical review.
- Hypersensitivity (see Section 14.1.6)
- Temporally-related events (TRE) (e.g. AEs with onset after initiation of a study drug infusion and within 24 hours of the start or restart of the infusion)

	BMN 190-203 Statistical Analysis Plan, Version 2.0	Pg. 41 of 53
---	---	--------------

- Device-related events (e.g., infection, prophylactic ICV replacement, malfunction with an associated AE such as leaking reservoir or a problem that ends the administration of study drug for that visit, etc)
- Cardiac and ECG events

It is defined to comprise the preferred terms within the SOCs of vascular disorders and cardiac disorders, the High Level Term of ECG investigations, and the HLGT of cardiac and vascular investigations.

Adverse events of special interest will be summarized in a similar manner to general adverse events.

14.2 Clinical Laboratory Tests

Clinical laboratory tests include chemistry, hematology, and urinalysis. Clinical laboratory test values and change from Baseline will be summarized descriptively by visit. Laboratory test values will be presented over time using boxplots.

Laboratory tests will also be summarized in terms of results relative to the lab reference ranges (low, high). Shift tables cross-tabulating the normal/abnormal results at Baseline vs. post-baseline visits will be provided as well. A supportive listing of abnormal test values will be produced.

14.3 Vital Signs

Vital signs include systolic blood pressure (BP), diastolic BP, heart rate, respiratory rate, and temperature. Vital signs will be summarized descriptively by visit using the maximum/minimum value for multiple assessments (e.g. during and pre- and post-infusion) at each visit. Vital signs will also be presented every 8 weeks using boxplots.

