- Vital signs (SBP, DBP, heart rate, respiration rate, and temperature) will be measured within 30 (±5) minutes before infusion start (or restart), every 30 (±5) minutes during infusion, 0.5 hours (±5 minutes), 1 hour (±5 minutes), and 4 hours (±15 minutes) after infusion end, and then every 4 hours (±15 minutes) for the next 16 hours. Blood pressure will be measured in the upper arm using an appropriately sized blood pressure cuff. If the patient's blood pressure is abnormal (as compared to site-specific reference ranges), a manual blood pressure will be obtained by a trained healthcare professional.

BOMARIN

^p Details on complete and brief physical examinations and neurological examination are provided in Section 9.7.5.

- ^q Collection of samples for clinical laboratory assessments should precede infusion. Collection will be every 4 weeks for 2 assessments (Weeks 1-9), every 8 weeks for 5 assessments (Weeks 17-49), and then continue at a frequency of every 12 weeks thereafter (Weeks 61-145).
- ^r OCT should precede infusions. In order to limit the need for sedation to perform this assessment, measurement should be obtained while the subject is also under sedation for MRI acquisition.
- ^s Quality of life will be assessed using the PedsQL (including both a Parent Report for Toddlers and a Family Impact Module) and a CLN2 disease-based QoL instrument. If done on the same day, assessment of QOL should precede MRI, infusion, and other procedures. PedsQL parent report for appropriate age of subject.

^t If done on the same day, assessment of the Denver II Scale should precede MRI and sampling.

- ^u All subjects will undergo Preferential Looking Testing every 12 weeks. In addition, for those children who retain the cognitive function to adhere to testing, the Lea Vision Test or E Hook (or Tumbling E) Vision Test should also be performed during the same assessment. Visual acuity testing can be performed either before or after the infusion (± 3 days), but should be performed at a time (relative to infusion) that can be repeated consistently between study visits. The subject must not be sedated at the time of visual acuity testing.
- ^v Pregnancy in a patient or partner should be reported within 24 hours of the site becoming aware of the pregnancy and will continue through 6 months after the last dose of study drug. Refer to Section 10.3.1.10 for further information.

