9.7.5 Vital Signs, Physical Examinations, and Other Observations

9.7.5.1 Vital Signs

Vital signs (SBP, DBP, heart rate, respiration rate, and temperature) will be measured within $30 (\pm 5)$ minutes before infusion start (or restart), every $30 (\pm 5)$ minutes during infusion, 0.5 hours (± 5 minutes), 1 hour (± 5 minutes), and 4 hours (± 15 minutes) after infusion end, and then every 4 hours (± 15 minutes) for the next 16 hours. Blood pressure will be measured in the upper arm using an appropriately sized blood pressure cuff. If the patient's blood pressure is abnormal (as compared to site-specific reference ranges), a manual blood pressure will be obtained by a trained healthcare professional.

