14.4 Safety Analysis

Safety analysis will be descriptive.

All AEs will be coded by BioMarin using the current version of MedDRA to assign system organ class and preferred term classification to events and diseases, based on the original terms entered on the CRF. The incidence of AEs will be summarized by system organ class, preferred term, relationship to study treatment, and severity.

Concomitant medications will be coded using World Health Organization Drug Dictionary and summarized.

BIOMARIN¹⁹⁰⁻²⁰³ Amendment 6

Clinical laboratory data will be summarized in terms of observed values and changes from Baseline. Lab data will also be summarized relative to categorical reference ranges (e.g., lab normal ranges and/or CTCAE grade).

Vital signs will be summarized in terms of observed values and changes from Baseline.

ECGs will be summarized in terms of investigator overall interpretation, abnormal findings, and quantitative intervals (QTcF, etc.).

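### Vital-sign extremes pooled over pre-, during- and post-infusion readings are not comparable with a single pre-dose Baseline reading (minor; one descriptive safety table)

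*SAP*

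**What the plan says.** SAP 14.3 reduces each visit to its extremes: "Vital signs will be summarized descriptively by visit using the maximum/minimum value for multiple assessments (e.g. during and pre- and post-infusion) at each visit". It adds boxplots every 8 weeks without saying which readings they use. It does not mention change from baseline, whereas SAP 14.2 (laboratory tests) and 14.4 (ECG) do.

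Protocol 14.4 does plan a change: "Vital signs will be summarized in terms of observed values and changes from Baseline". Protocol 14.1 gives the SAP precedence where the two differ.

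The readings come from Protocol 9.7.5.1 and the footnotes to Table 9.1.1. There is one before the infusion starts or restarts, followed by readings "every 30 (±5) minutes during infusion". Three early readings are due half an hour, one hour and four hours once the infusion has finished. A late series completes the schedule: "and then every 4 hours (±15 minutes) for the next 16 hours".

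SAP 4.4 takes baseline as the last value before study drug. In SAP Appendix 1 the vital-signs Baseline row is Day 1 pre-dose and the Day 1 row is post-dose. From Week 3 each visit has one window with no split at the start of infusion. Neither document defines a baseline extreme to set against the visit extremes.

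**The concern.** The largest of many readings lies above a typical single reading by chance, and the smallest lies below it. A by-visit table that opens with a one-reading Baseline row and continues with rows of extremes therefore shows vital signs rising and falling after treatment, whatever the drug does. The study has a single arm, so no control column would reveal the same pattern.

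A second weakness starts at Week 3. Once the pre-infusion reading is pooled with the later ones, a reader cannot tell whether a visit's extreme came before or after drug entered. The reading count also varies with infusion length, so the size of the chance shift varies slightly with dose and age.

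At stake is how readers interpret blood pressure, heart rate and temperature around infusion. The protocol lists fever and blood-pressure change among the symptoms of hypersensitivity.

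**Working it through.** The documents state no figure for this point, so there is none to reproduce.

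**Step 1: readings per infusion visit.** Count = 1 before + readings every 30 minutes during infusion + 3 early after (0.5, 1 and 4 hours) + 4 late after (every 4 hours for 16 hours). Infusion times are from Protocol Table 9.4.1.1.

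| Infusion time | During infusion | Total readings |
|---|---|---|
| 1.3 h | 2 | 1+2+3+4 = 10 |
| 2 h | 3–4 | 11–12 |
| 2.7 h | 5 | 1+5+3+4 = 13 |
| 4 h | 8 | 1+8+3+4 = 16 |

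The lower count at 2 h omits a reading exactly at infusion end. On that convention the 4-hour total is 15.

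**Step 2: expected shift with no drug effect.** Assume normal readings about a stable patient mean, measured in units of the within-patient SD. One baseline reading has expectation 0. The maximum of n independent readings has expectation E[max] = ∫ x·n·φ(x)·Φ(x)^(n−1) dx, and the minimum mirrors it.

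| n | E[max], SD units |
|---|---|
| 10 | 1.54 |
| 13 | 1.67 |
| 15 | 1.74 |
| 16 | 1.77 |

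**Step 3: serial correlation.** Readings half an hour apart are not independent. The 16 readings were simulated at their scheduled times (200,000 draws) with correlation exp(−gap/τ), against a baseline reading that fluctuates independently about the same mean.

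| Correlation | Mean shift of maximum | Maximum above Baseline | Both extremes cross Baseline |
|---|---|---|---|
| Independent | 1.77 | 94% | 88% |
| τ = 1 h | 1.65 | 92% | 84% |
| τ = 2 h | 1.54 | 91% | 81% |
| τ = 4 h | 1.40 | 88% | 75% |

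The minimum falls by nearly the same amounts (1.39 at τ = 4 h), so the range is about 1.4 to 1.8 SD. Day 1 is affected as well: the maximum of 15 post-dose readings against the one pre-dose reading gives 1.36 to 1.74 SD.

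**Step 4: what this could mean in clinical units.** The documents give no within-patient SD. If the systolic SD were 5, 8 or 10 mmHg (an assumption), 1.4 to 1.8 SD would be about 7–9, 11–14 or 14–18 mmHg in each direction.

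**Step 5: difference between infusion lengths.** 16 readings against 10: 1.77 − 1.54 = 0.23 SD.

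**Step 6: like-for-like comparison.** One pre-infusion reading at a later visit against the one pre-dose Baseline reading gives an expected change of 0.00 SD.

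**The case against.** The strongest reply is that the comparison with Baseline is not in SAP 14.3. That section plans observed extremes only, Protocol 14.4 plans a change without mentioning extremes, and the SAP prevails where they differ. A reader might infer that the SAP prescribes subtracting a single baseline reading from a visit extreme. The documents do not say so. What stands is narrower: the SAP is silent rather than contradictory, and its own windows still put a one-reading Baseline row beside rows of extremes.

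Four other stronger readings also fail.

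- **Distorted trends over time.** From Week 3 the window structure is the same at each two-weekly visit. For a fixed infusion length extremes sit beside extremes, and the chance shift largely cancels.
- **Age and dose groups that cannot be compared.** The gap is at most about 0.2 SD on these counts. Shorter infusions are scheduled only below 1 year of age and for the first 4 doses from 1 to under 2 years.
- **A real excursion being hidden.** This is not shown. An extreme over all readings keeps every spike and dip, which is the purpose of a worst-value screen. What is lost is its timing.
- **Safety conclusions depending on this table.** Events of special interest, temporally related events and hypersensitivity events are summarised from coded adverse events (SAP 14.1.6 and 14.1.7). ECG has threshold counts and a shift table (SAP 14.4). Safety is descriptive with no formal inference (SAP 14).

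It is also fair to say that a same-visit reference does not isolate the drug. Antihistamine, and sedation where used, is given about 30 minutes before infusion, close to the pre-infusion reading.

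**Conclusion.** The point holds as a minor one about a single descriptive table. Any comparison of a visit's extremes with the Day 1 pre-dose value carries a no-effect rise in the maximum and fall in the minimum of about 1.4 to 1.8 within-patient SD for a 4-hour infusion. From Week 3 the table also cannot place an extreme before or after drug start.

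The SD-unit size rests on roughly normal readings about a stable patient mean, with correlation that fades over hours. The direction follows from comparing an extreme with a single reading. No particular shift in mmHg or bpm can be claimed, because the SD is not in the documents.

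**What to change.** Amend SAP 14.3 in three places.

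- **(a)** Use the pre-infusion reading at each visit for the by-visit trend and for change from Baseline. This is like-for-like and also states explicitly the change that Protocol 14.4 plans.
- **(b)** Take the maximum and minimum over readings after the start of infusion only. Report them as change from that visit's own pre-infusion reading, label them as extremes, and show them apart from the Baseline row. They still compare an extreme with one reading (the Day 1 calculation gives 1.36 to 1.74 SD), so the label matters. They serve as a worst-value screen and should not be read as an average effect.
- **(c)** Add change from the same visit's pre-infusion reading at the scheduled times during and after infusion, with a note that premedication is given near the reference reading. Fixed times can miss a brief excursion between them, which is the reason to keep (b).

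The SAP should also say which readings the boxplots use.

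The data are already collected, so the cost is SAP wording, table programming and more rows per table.

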14.4 Electrocardiogram (ECG)

Quantitative ECG (12-lead) parameters (heart rate, RR, PR, QRS, QTcB, and QTcF) and change from baseline will be summarized by visit. QTcF and QTcB will be further summarized in terms of the number of subjects with observed values >450, >480, or >500 msec, or with changes from baseline >30 or >60 msec.

The number of subjects with one or more ECGs that are judged abnormal, and clinically significantly abnormal, will be summarized.

The overall interpretation from investigator ECGs will be cross tabulated using a shift table at baseline vs. post-baseline results.

BIOMARIN®	BMN 190-203 Statistical Analysis Plan, Version 2.0	Pg. 42 of 53
------------------	---	--------------

For the first infusion of BMN 190, continuous ECG monitoring (3- or 5-lead) is performed for all subjects. In the event that the subject has already received the first infusion of BMN 190, the next infusion is monitored. If a 12-lead ECG is required during this time, continuous monitoring will be interrupted in order to obtain the 12-lead ECG. The 3- or 5-lead ECG data in Study will be provided in a listing.

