10.1.3 Adverse Events of Special Interest (AEoSI)

The following AEoSI need to be reported to the Sponsor within 24 hours of site awareness, irrespective of seriousness, severity or causality, to facilitate real-time monitoring and assessment:

- Status epilepticus
- Hydrocephalus (communicating and non-communicating)
- Meningitis
- Unexpected rapid decline on CLN2 scale not attributable to other causes
- Hypersensitivity
- Temporally-related events
- Device-related events (e.g., infection, prophylactic ICV replacement, malfunction with an associated AE such as leaking reservoir or a problem that ends the administration of study drug for that visit, etc).
 - All removed or replaced implantable ICV devices must be returned to BioMarin in order to evaluate the material integrity of the reservoir, and all other devices (as described in the protocol Pharmacy Manual) except for infusion pumps, should also be returned.
- Cardiovascular events
- ECG adverse events

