3.4 Study Dosage and Administration

BMN 190 is administered every 14 days from the date of the first infusion (± 3 days) for at least 144 weeks according to the subject's age:

- birth to < 6 months: 100 mg
- 6 months to < 1 year: 150 mg
- 1 year to < 2 years: 200 mg (first 4 doses), 300 mg (subsequent doses)
- ≥ 2 years: 300 mg

	BMN 190-203 Statistical Analysis Plan, Version 2.0	Pg. 13 of 53
---	---	--------------

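### SAP 14.4 gives heart rate, RR, PR and QRS no age reference, so change at the 24-weekly ECG visits cannot separate growth from a drug effect

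*SAP*

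**What the plan says.** SAP 14.4 sets out the quantitative ECG output: "Quantitative ECG (12-lead) parameters (heart rate, RR, PR, QRS, QTcB, and QTcF) and change from baseline will be summarized by visit". It then applies one set of cut-offs at every age: "QTcF and QTcB will be further summarized in terms of the number of subjects with observed values >450, >480, or >500 msec". The rest of that sentence sets the limits for change, again the same for all children: "or with changes from baseline >30 or >60 msec".

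Two outputs rest on the reader's judgement of the tracing: "The number of subjects with one or more ECGs that are judged abnormal, and clinically significantly abnormal, will be summarized", and "The overall interpretation from investigator ECGs will be cross tabulated using a shift table at baseline vs. post-baseline results".

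The setting comes from other sections:

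- **Age at entry.** Protocol 9.3 admits children from birth. SAP 3.2 plans at least 5 who are younger than 2 years.
- **Duration.** SAP 3.4 has dosing "for at least 144 weeks according to the subject's age".
- **ECG schedule.** Protocol 9.1 has a 12-lead ECG after the first infusion and then every 24 weeks.
- **Importance.** Protocol 10.1.3 lists cardiovascular events and "ECG adverse events" among the events of special interest.
- **Protocol analysis text.** Protocol 14.4 mentions the intervals briefly and gives QTcF as its example.
- **Comparator.** SAP section 13 limits the matched historical comparison to the CLN2 scales.

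**The concern.** A raw change from baseline can be read as a treatment signal only if little would have changed without treatment. Over nearly three years of early childhood that is doubtful for heart rate, RR, PR and QRS. This is a single-arm study, so no ECG column shows what untreated children of the same age would do. A drift at Week 97 or Week 145 could be growth, drug or both, and the table cannot say which.

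The youngest children matter most here. The earlier study enrolled from age 3 (Protocol 7.2), so those under 2 are a new exposure group.

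The SAP already has a better pattern next door. Section 14.2 sets laboratory values against reference ranges and adds a baseline shift table. ECG intervals get neither.

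QTcB is the second strand. It varies with heart rate even when QTcF is unchanged, so a fixed QTcB cut-off does not mean the same thing at infant and toddler heart rates.

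**Working it through.** **Inputs from the documents.** Treatment lasts at least 144 weeks; the cut-offs are 450/480/500 msec observed and 30/60 msec change.

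**Assumed inputs.** The documents give no paediatric heart rates, interval norms or QTcF levels. I take QTcF at 400 msec, and heart-rate falls with age from 140 to 100 down to 100 to 90/min. The documents give nothing from which to size PR or QRS drift, so I give no figure for those.

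**Duration.** 144 x 7 / 365.25 = 2.76 years. A child who enters at 6 months (assumed) is about 3.3 years old at the end.

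**QTc relation.** With RR = 60/heart rate in seconds, QTcB = QT/RR^(1/2) and QTcF = QT/RR^(1/3). Hence QTcB = QTcF x RR^(-1/6).

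- At 140/min, RR = 0.4286 and the factor is 1.152, so QTcB = 460.7.
- At 100/min, RR = 0.600 and the factor is 1.089, so QTcB = 435.5.

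**No drug effect, QTcF constant at 400 msec** (changes use unrounded values):

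| Heart rate (/min) | RR change (msec) | QTcB start | QTcB end | QTcB change | True QTcF rise needed for QTcB +30 |
|---|---|---|---|---|---|
| 140 to 100 | +171 | 460.7 | 435.5 | -25.1 | 50.6 |
| 130 to 100 | +138 | 455.0 | 435.5 | -19.5 | 45.4 |
| 120 to 100 | +100 | 449.0 | 435.5 | -13.4 | 39.9 |
| 100 to 90 | +67 | 435.5 | 428.0 | -7.6 | 35.1 |

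The last column is (starting QTcB + 30) / (factor at the final heart rate) - 400.

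**When an unchanged QTcF passes the QTcB 450 cut-off.** The heart rate must exceed 60 x (450/QTcF)^6. That is 122/min for QTcF 400 and 142/min for QTcF 390.

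**Reverse assumption.** Suppose QT follows Bazett and QTcB stays at 400 msec. Then QTcF = 400 x RR^(1/6), which goes from 347.3 to 367.4 (+20.0) for 140 to 100/min, and from 356.4 to 367.4 (+11.0) for 120 to 100/min. QTcF is not immune to the same drift.

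**Which comparisons are affected.** The Appendix 1 windows separate Baseline from a Day 1 ECG at 30 minutes. Protocol 9.1 places the Baseline visit no more than 2 days before the first infusion. Growth cannot matter over that span. It can at Week 25 and every later visit.

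**The case against.** The strongest reply is that the plan already has several ways to find a cardiac effect.

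- **QTcF sits in the same output with identical cut-offs.** In the 140 to 100/min case, a true QTcF rise between 30 and about 50 msec would be missed by the QTcB change count but caught by the QTcF one. This stands. A reader might infer that the plan will miss real prolongation; the documents do not support that.
- **Judgement-based outputs exist.** These are the abnormal and clinically significant counts, the investigator shift table and the special-interest event summaries in SAP 14.1.7. This stands for gross abnormality. These outputs classify whole tracings or events, and would not show a modest group shift in PR, QRS or heart rate beyond what age explains.
- **Growth-free contrasts exist.** Baseline to Day 1 is one. Children with bradycardia, conduction disorders or structural heart disease also have ECGs around each infusion (Protocol 9.1). This stands for acute effects only.
- **Age columns are planned.** SAP 4.2 splits safety tables at <2, <3 and >=3 years. This is partial. The first two columns overlap, so 2-<3 is never shown alone, and children go on ageing inside each column.

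A reader might also infer that ageing mimics QT prolongation. In the computed range it lowers QTcB, so it creates no false rise above 30 or 60 msec. The mimicry is confined to high early QTcB values and to heart-rate and RR drift. Nor is every infant flagged: at 120/min the assumed QTcB is 449.0 msec, just under the cut-off.

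**Conclusion.** The point holds as a cheap improvement. For heart rate, RR, PR and QRS, change at the 24-weekly visits cannot be attributed, because there is no age reference and no ECG control. That conclusion follows from the design, together with the ordinary assumption that these measures change as young children grow.

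The QTcB strand is secondary. Under the assumed heart rates, QTcB drifts by -7.6 to -25.1 msec with no drug effect, and hides about 5 to 21 msec of a true rise at the 30 msec cut-off (35.1 - 30 to 50.6 - 30). The planned QTcF counts limit the consequence. The documents do not say how many children enter under 1 year, so the 140/min case may apply to few or none.

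Three stronger conclusions are not supported. The documents do not describe the cut-offs as adult values. QTcB is not a departure from the protocol, whose wording is open-ended ("ECGs will be summarized in terms of investigator overall interpretation, abnormal findings, and quantitative intervals (QTcF, etc") and which lets the SAP prevail. Removing QTcB from the tables would lose a cross-check, since QTcF drifts by +11 to +20 msec under the reverse assumption.

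Safety reporting is descriptive (SAP section 14), so no test, population or efficacy endpoint is affected.

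**What to change.** In SAP 14.4:

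- For heart rate, PR and QRS, add the number of children below or above a named set of age-specific limits at each ECG, using age at that ECG. Age z-scores would also serve.
- Add a shift from baseline category (below, within, above), following the laboratory approach in SAP 14.2.
- Show these by the non-overlapping baseline age groups of SAP section 8: <2, 2-<3 and >=3 years.
- Keep the raw by-visit table and both QTc corrections. Present QTcF first, as it is the correction that the protocol names.

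The cost is choosing and citing one reference table and programming one more descriptive output. No new data are needed, and no clinical rule changes.
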